9.3.6 Laboratory tests

Laboratory tests will be performed at the central laboratory. The investigator or subinvestigator will collect blood and urine samples from participants before study treatment initiation and submit them to the central laboratory. Tuberculosis test may be performed in an in-hospital laboratory.

- Hematology and serum chemistry tests
- Immunological tests (thymus and activation-regulated chemokines [TARC])
- Urinalysis

Time points	Day of screening, Day of study treatment initiation, Week 1, 4, 8, 12, 16, 20, 24, 28, 32, 36, 40, 44 and 48, Week 52 or Day of discontinuation visit, Day of follow-up visit
Notes	
 1) 2) and 3): 
 On the day of study treatment, blood and urine will be collected before the treatment. The test result should be reviewed before the next study treatment. 1) and 2): 
 When aggregation or coagulation is observed in "Plt" because of a reason other than manual technique, blood will be collected into a blood collecting tube containing 3.2% sodium citrate in addition to a conventional blood collection tube from the next visit.

4) Pregnancy test

Time points	Day of screening
Notes	
 The test will be performed on female participants. However, those who are considered unable to become pregnant (e.g., menopausal women* and women who have had total hysterectomy) will be excluded. *: Defined as those who are amenorrhea for at least 12 months without any medical reason.

5) Tuberculosis test

Time points	Day of screening
Notes	
 If the test cannot be performed on the day of screening, it may be performed on another day after the day of screening but before study treatment initiation. In such cases, the rest results should be reviewed before administration of IP on the day of study treatment initiation.

6) Hepatitis B and C tests

Time points	a) Day of screening b) Week 12, 24, 36 and 48, Day of follow-up visit
Notes	a) The participants who test negative for HBs antigen and positive for HBc antibody on the day of screening will undergo HBV-DNA measurement before the day of study treatment initiation. The participants who test positive for anti-HCV antibody on the day of screening will undergo HCV-RNA measurement before the day of study treatment initiation. b) The participants enrolled through HBV-DNA measurement before the day of study treatment initiation will undergo HBV-DNA measurement once every three months. The participants enrolled through HCV-RNA measurement before the day of study treatment initiation will undergo HCV-RNA measurement once every three months.

7) Antinuclear antibodies test

Time points	Day of study treatment initiation
Notes	
 Blood will be collected before administration of IP on the day of study treatment initiation

Table 9-2: Clinical Laboratory Assessments

Laboratory tests	Parameters
Hematology	Hb, Ht, Plt, RBC, WBC, differential leukocyte count, MCV, MCH, and MCHC
Serum chemistry	Na, K, Cl, UN, CREA, Ca, T-Bil, D-Bil, TP, ALB, ALT (GPT), AST (GOT) , ALP, P, LDH, CK, UA, TC, LDL-C, HDL-C, TG, A/G ratios, γ -GTs, and CRP
Immunology	TARC
Urinalysis	Protein, occult blood, urinary sugar, and urobilinogen
Pregnancy	Urine hCG
Tuberculosis	Interferon gamma release assay (Central measurement: T-SPOT, in-house examination: T-SPOT or QFT-3G)
Hepatitis B and C	HBs antigen, HBc antibody, HBV-DNA, Anti-HCV antibody, and HCV-RNA
Antinuclear antibodies	Anti-Scl-70 antibodies, anti-centromere antibodies, and anti-RNA polymerase-III antibodies

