5.2.2 Discontinuation after Enrollment

- 1) The investigator or subinvestigator will explain the reason to withdraw the participant from the study and take appropriate action, ascertain and record the reason for discontinuation in the source documents.
- 2) The investigator or subinvestigator will perform the observation/tests scheduled on the day of visit for discontinuation. When determining to discontinue the study on a day other than the day of the visit, the investigator or subinvestigator will instruct the participant to come to the study site as early as possible. However, if the day of visit for discontinuation is on or after 77 days from the last dose of study treatment.
- 3) The investigator, subinvestigator, or CRC will record the data of the items described in Section 19.1.1 in the CRF.

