9.3.14 Amount of Blood and Urine Samples to be Collected

In principle, the amounts of blood and urine samples to be collected on each assessment day will follow [Table 9-3](#) unless additional tests are required.

Table 9-3: Amount of blood and urine samples to be collected

1)		Day of screening*	Day of treatment initiation	Week 1	Week 2	Week 4	Week 8, 16 and 20	Week 12**	Week 24**, and Week 52 or Day of discontinuation visit	Week 28, 32, 40, 44 and 48**	Week 36	FU**
Amount of blood collected	Laboratory tests	17 mL	6 mL	6 mL	-	6 mL	6 mL	6 mL	6 mL	6 mL	6 mL	6 mL
	Serum nemolizumab concentration	-	3 mL	3 mL	3 mL	3 mL	3 mL	3 mL	3 mL	-	3 mL	3 mL
	Anti-nemolizumab antibody	-		-	-	-	-	-		-	-	
	Antinuclear antibodies test	-	6 mL	-	-	-	-	-	-	-	-	-
	Biomarker measurement	-	12 mL	-	-	9 mL	3 mL	12 mL	12 mL	-	9 mL	-
	Comprehensive measurement of autoantibodies	-	5 mL	-	-	-	-	-	5 mL	-	-	-
	CyToF measurement	-	5 mL	-	-	-	-	-	5 mL	-	-	-
Total amount of blood collected		17 mL	37 mL	9 mL	3 mL	18 mL	12 mL	21 mL	31 mL	6 mL	18 mL	9 mL
Amount of urine collected		10 mL	10 mL	10 mL	-	10 mL	10 mL	10 mL	10 mL	10 mL	10 mL	10 mL

* : The participants found to require measurement of HBV-DNA or HCV-RNA as a result of the hepatitis B and hepatitis C tests performed on the day of screening will need an additional 5 mL of blood to be drawn before the day of study treatment initiation.

** : The participants enrolled through HBV-DNA or HCV-RNA will need an additional 5 mL of blood to be drawn on Week 12, 24, 36 and 48, and on the day of follow up visit.

10. Efficacy Evaluation

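### HBV-DNA/HCV-RNA retesting is due every three months, but no viral test is scheduled at the discontinuation visit, so some early stops leave a nominal 112 or 140 days until the follow-up test

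*Combined protocol and SAP*

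**What the plan says.** The file holds three versions of the protocol. References here are to the one whose study period runs to November 2024.

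- **Who is concerned.** Exclusion criterion 9 (Section 4.3) admits patients positive for HBc antibody (HBs antigen negative) or for anti-HCV antibody if a pre-treatment viral test shows no infection. Under Notes a) of Section 9.3.6 6), the hepatitis B group "will undergo HBV-DNA measurement before the day of study treatment initiation". The first footnote of Table 9-3 says that anyone needing either test "will need an additional 5 mL of blood to be drawn before the day of study treatment initiation".
- **The rule.** Under Notes b), those enrolled this way "will undergo HBV-DNA measurement once every three months", and likewise for HCV-RNA. Footnote h of Table 9-1 repeats it.
- **The schedule.** Time points b) read "Week 12, 24, 36 and 48, Day of follow-up visit". In Tables 4-1 and 9-1 the hepatitis row has conditional marks at those visits and a blank in the shared Week 52/discontinuation column. The second footnote of Table 9-3 agrees: an "additional 5 mL of blood to be drawn on Week 12, 24, 36 and 48, and on the day of follow up visit".
- **The contrast.** Hematology, serum chemistry, TARC and urinalysis are scheduled through "Week 52 or Day of discontinuation visit, Day of follow-up visit".
- **What happens at a stop.** Section 5.2.2 tells the site to "perform the observation/tests scheduled on the day of visit for discontinuation". Section 9.2.8 and footnote j of Table 9-1 then place follow-up 84 days (±7) after the last dose.

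**The concern.** The schedule suits a completer, who needs no viral test at Week 52. Because Week 52 and discontinuation share one column, leaving it blank also removes the test for someone who stops early. The follow-up test then comes at a fixed distance from the last dose, however long ago the last viral test was.

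The stake is safety monitoring. Section 4.3 gives participant safety as the reason for criterion 9, and periodic viral testing is the condition attached to its exceptions. The ban on immunosuppressants ends at the discontinuation examination (Section 8.4.3), and SSc drugs newly started from then on need not be recorded for these participants (Section 9.3.2.1). A participant withdrawn for inadequate response could therefore change treatment during the untested stretch.

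**Working it through.** **Inputs (Table 9-1, Section 8.1).** Doses on Day 1 and every 4 weeks to Week 48. Reference days: Week 12 = 85, 16 = 113, 20 = 141, 24 = 169, 28 = 197, 32 = 225, 36 = 253, 40 = 281, 44 = 309, 48 = 337. Windows: ±3 days at Weeks 4 to 16, ±7 from Week 20 and at follow-up. Section 9.2.3 has no Day 0.

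**The plan's own figures.** Reference day = 7 × week + 1 matches every listed day. Viral tests are 169 − 85 = 253 − 169 = 337 − 253 = 84 days apart. Week 48 to follow-up is (337 + 84) − 337 = 84. A last dose at Week 12, 24 or 36 also gives 84.

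**Formula.** Gap = (day of last dose + 84) − day of last viral test, for a participant who withdraws before the next viral test.

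| Last dose | Last viral test | Nominal gap (days) | With all windows |
|---|---|---|---|
| Week 16 | Week 12 | 113 + 84 − 85 = 112 | 99 to 125 |
| Week 28 | Week 24 | 197 + 84 − 169 = 112 | 91 to 133 |
| Week 40 | Week 36 | 281 + 84 − 253 = 112 | 91 to 133 |
| Week 20 | Week 12 | 141 + 84 − 85 = 140 | 123 to 157 |
| Week 32 | Week 24 | 225 + 84 − 169 = 140 | 119 to 161 |
| Week 44 | Week 36 | 309 + 84 − 253 = 140 | 119 to 161 |

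Window limits, for example at Week 28: (190 + 77) − 176 = 91 and (204 + 91) − 162 = 133. At Week 32: (218 + 77) − 176 = 119 and (232 + 91) − 162 = 161.

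**Benchmark.** The protocol does not define three months in days. A quarter of a year is about 91 days. Its own windows allow (253 + 7) − (169 − 7) = 98 days between the Week 24 and Week 36 tests. The 140-day case exceeds both even at its minimum of 119; the 112-day case can shrink to 91.

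**If the next test is drawn.** For a last dose at Week 20 with the Week 24 test done, follow-up is 225 − 169 = 56 days later. The same holds for Weeks 32 and 44.

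**Stops before Week 12.** The only earlier viral test is pre-treatment, at the latest on Day -1, one day before Day 1.

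- Last dose Day 1: follow-up on Day 85, gap 85 nominal, minimum 78 (follow-up on Day 78).
- Last dose Week 4 (Day 29): follow-up on Day 113, gap 113 nominal, minimum 103 (26 + 77).
- Last dose Week 8 (Day 57): follow-up on Day 141, gap 141 nominal, minimum 131 (54 + 77).

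If the test was on nominal screening Day -14, the nominal gaps are 84 + 14 = 98, 112 + 14 = 126 and 140 + 14 = 154.

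**The case against.** The strongest reply is that the plan contains no contradiction. The three-month rule is not switched off at discontinuation, Section 9.3.14 allows more blood "unless additional tests are required", and the CRF takes unscheduled visits (Section 19.1.1). A careful site could test on time. This stands, and it rules out the stronger inference that the protocol drops the obligation for early stoppers. What remains is that no listed visit, table cell or blood allotment carries the obligation out on this path.

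Second, a reader might infer that any stop after a last dose at Week 20, 32 or 44 means 140 days. It does not. The next dosing visit is itself a viral-test visit, and tests precede dosing (Section 8.3), so the case needs withdrawal before that test is drawn. A discontinuation visit inside the Week 24, 36 or 48 window also puts the participant on site when a test is listed. Section 17.2.1 counts such data towards that period, although as an analysis rule it does not order the test.

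Third, the clinical weight is small. AST, ALT and bilirubin are measured at discontinuation and follow-up, with adverse-event thresholds in Section 11.3. Dosing has stopped, and Section 8.3 gives a half-life of 12.6 to 14.6 days. A reader might infer a demonstrated risk of viral reactivation with nemolizumab; no statement of that kind in the protocol is relied on here. The liver tests are nevertheless only a partial safeguard, because they do not measure viral load.

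**Conclusion.** The concern holds, at minor severity. For participants enrolled through HBV-DNA or HCV-RNA testing who stop between viral tests, following the listed schedule does not deliver the protocol's own interval. The nominal gap is 112 days for last doses at Weeks 16, 28 and 40, and 140 days for Weeks 20, 32 and 44. For last doses at Weeks 4 and 8 it is 113 and 141 days from a Day -1 test. These are nominal values, not minima. A last dose on Day 1 is not a shortfall from a Day -1 test, and completers are not affected.

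This assumes that withdrawal comes before the next viral test, that follow-up takes place as scheduled, and that the site adds no unscheduled test. The documents do not say how many of the 8 participants enter through viral testing; it may be none. There is no effect on the efficacy analysis.

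**What to change.** For participants enrolled through HBV-DNA or HCV-RNA testing only:

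1. Add the day of the discontinuation visit to time points b) in Section 9.3.6 6).
2. Put a conditional mark, for discontinuation only, in the Week 52/discontinuation cell of the hepatitis row in Tables 4-1 and 9-1.
3. Add that visit to the extra 5 mL footnote of Table 9-3.

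Example: last dose on Day 141 and discontinuation visit on Day 155, outside the Week 20 window (Days 134 to 148) and the Week 24 window (Days 162 to 176). The intervals become 155 − 85 = 70 and 225 − 155 = 70 days instead of 140.

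The change shortens the gap but sets no fixed maximum. After a last dose at Week 20, 32 or 44, a decision 27 days later plus the 14-day allowance gives 56 + 27 + 14 = 97 days to the discontinuation test. From a Day -14 test, a decision on Day 84 and a visit on Day 98 give 14 + 97 = 111 days.

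The cost is a small amendment and, per affected participant, one 5 mL sample and assay at a visit where Table 9-3 already draws 31 mL. No visit is added, and completers need no extra test.

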9.3.7 Pharmacokinetics

The investigator or subinvestigator will collect blood samples for central measurement of serum drug concentrations.

To be measured	Serum concentration of nemolizumab
Time points	Day of study treatment initiation, Week 1, 2, 4, 8, 12, 16, 20, 24, and 36, Week 52 or Day of discontinuation visit, Day of follow-up visit
Notes	• On the day of study treatment, blood will be collected before the treatment.

9.3.8 Immunogenicity

The investigator or subinvestigator will collect blood samples for central measurement of serum anti-nemolizumab antibodies and neutralizing antibodies.

To be measured	Serum anti-nemolizumab antibodies and neutralizing antibodies
Time points	Day of study treatment initiation, Week 24 and 36, Week 52 or Day of discontinuation visit, Day of follow-up visit
Notes	• On the day of study treatment, blood will be collected before the treatment.

9.3.9 Biomarker measurement

The investigator or subinvestigator will collect blood samples for central measurement of serum biomarkers.

To be measured	1) IL-31 2) KL-6, SP-D, NT-proBNP 3) Exploratory biomarkers
Time points	1) Day of study treatment initiation, Week 4, 8, 12, 16, 20, 24, and 36, Week 52 or Day of discontinuation visit 2) Day of study treatment initiation, Week 4, 12, 24, and 36, Week 52 or Day of discontinuation visit 3) Day of study treatment initiation, Week 12 and 24, Week 52 or Day of discontinuation visit
Notes	1) 2) 3) :

	On the day of study treatment, blood will be collected before the treatment
--	---

9.3.10 Comprehensive measurement of autoantibodies

The investigator or subinvestigator will collect blood samples for comprehensive measurement of autoantibodies. The measurement will be performed centrally.

Time points	Day of study treatment initiation, Week 24, Week 52 or Day of discontinuation visit
Notes	• On the day of study treatment, blood will be collected before the treatment.

9.3.11 CyTOF measurement

The investigator or subinvestigator will collect blood samples for central measurement of CyTOF.

Time points	Day of study treatment initiation, Week 24, Week 52 or Day of discontinuation visit
Notes	• On the day of study treatment, blood will be collected before the treatment.

9.3.12 Assessment of Adverse Events

The investigator or sub-investigator will assess the adverse events according to the procedure described in “[11.4 Review and reporting of adverse events.](#)”

9.3.13 Investigation of Malfunction of DCS

The investigator or subinvestigator will investigate malfunction of DCS according to "[11.11 Malfunctions of DCS.](#)"

9.3.14 Amount of Blood and Urine Samples to be Collected

In principle, the amounts of blood and urine samples to be collected on each assessment day will follow [Table 9-3](#) unless additional tests are required.

Table 9-3: Amount of blood and urine samples to be collected

1)		Day of screening*	Day of treatment initiation	Week 1	Week 2	Week 4	Week 8, 16 and 20	Week 12**	Week 24**, and Week 52 or Day of discontinuation visit	Week 28, 32, 40, 44 and 48**	Week 36	FU**
Amount of blood collected	Laboratory tests	17 mL	6 mL	6 mL	-	6 mL	6 mL	6 mL	6 mL	6 mL	6 mL	6 mL
	Serum nemolizumab concentration	-	3 mL	3 mL	3 mL	3 mL	3 mL	3 mL	3 mL	-	3 mL	3 mL
	Anti-nemolizumab antibody	-		-	-	-	-	-		-	-	
	Antinuclear antibodies test	-	6 mL	-	-	-	-	-	-	-	-	-
	Biomarker measurement	-	12 mL	-	-	9 mL	3 mL	12 mL	12 mL	-	9 mL	-
	Comprehensive measurement of autoantibodies	-	5 mL	-	-	-	-	-	5 mL	-	-	-
	CyToF measurement	-	5 mL	-	-	-	-	-	5 mL	-	-	-
Total amount of blood collected		17 mL	37 mL	9 mL	3 mL	18 mL	12 mL	21 mL	31 mL	6 mL	18 mL	9 mL
Amount of urine collected		10 mL	10 mL	10 mL	-	10 mL	10 mL	10 mL	10 mL	10 mL	10 mL	10 mL

* : The participants found to require measurement of HBV-DNA or HCV-RNA as a result of the hepatitis B and hepatitis C tests performed on the day of screening will need an additional 5 mL of blood to be drawn before the day of study treatment initiation.

** : The participants enrolled through HBV-DNA or HCV-RNA will need an additional 5 mL of blood to be drawn on Week 12, 24, 36 and 48, and on the day of follow up visit.

10. Efficacy Evaluation

10.1 Efficacy Assessments

10.1.1 Assessment of Skin Findings

1) Modified Rodnan Total Skin Thickness Score (mRSS)

The investigator or subinvestigator will assess the degree of skin thickening for each of 17 sites (fingers of both hands, dorsum of both hands, both forearms, both upper arms, face, anterior chest, abdomen, both thighs, both lower legs, and dorsum of both feet) with a 4-point scale from 0 to 3 according to [Table 10-1](#) on each specified day of assessment. Total score will be 0 to 51.

Table 10-1 Scoring the degree of skin thickening by two-step pinching method

Score	Skin thickening	Broad pinching	Slight pinching	Skin thickness when pinched broadly
0	Normal	Possible	Possible	Not thick
1	Mild	Possible	Possible	Thick
2	Moderate	Possible	Impossible	Thicker
3	Severe	Impossible	Impossible	–

10.1.2 Respiratory Function Test

Spirographic examinations, including the flow-volume curve, lung volume measurements, and diffusing lung capacity for carbon monoxide (DL_{CO}) will be performed on each specified day of testing.

10.1.3 Chest HRCT

Chest HRCT will be performed to obtain visually the approximate ratios (HRCT extent) of interstitial opacities (ground-glass opacities, reticular shadows, honeycomb pattern and cystic shadows) with five slides of a) upper aortic arch, b) carina, c) pulmonary vein confluence point, d) midway between c) and e), and e) immediately above the right diaphragm, and their mean will be calculated.

The investigator or subinvestigator will assess in which of the following ranges the ratios are included; 20% or less ($\leq 20\%$), more than 20% to 70% or less ($> 20\%$ to $\leq 70\%$), or more than 70% ($>70\%$). In addition, in combination with FVC, each severity classification of lung disease will be determined according to [10.1.4 Severity Classification of Lung Lesion](#).

10.1.4 Severity Classification of Lung Lesion

The investigator or subinvestigator will assess the severity of lung lesions using the severity classification of lung lesions specified in the Guidelines for Diagnostic Criteria, Severity Classification and Clinical Practice of Systemic Sclerosis 2016⁷⁾ (see Figure 10-2). Respiratory function test results obtained according to [Section 10.1.2](#) and chest CT images obtained according to [Section 10.1.3](#) will be used for this assessment.

[figure not shown]

Figure 10-1 Severity classification of lung lesion

10.1.5 ACR-CRISS

ACR-CRISS is a composite outcome measure that is calculated as an index taking a value ranging from 0 to 1 for the probability of improving for participants based on the presence or absence of renal, pulmonary, and cardiac impairments and changes in the 5 core set items (mRSS, %FVC, PGA, PtGA, and HAQ-DI). Participants are considered improved and not improved when their ACR-CRISS is ≥ 0.6 and < 0.6 , respectively. If participants meet any of the following criteria, the probability of improving is 0.0. The investigator or subinvestigator will assess whether participants met or not met the following criteria at specified visits. If patients do not meet any of the following criteria, an ACR-CRISS score will be calculated using the formula shown in 17.3.2 2).

- Onset of scleroderma renal crisis
- Decline in FVC% $\geq 15\%$ (requiring reevaluation within 1 month), and %FVC of 80% or less
- Onset of left ventricular failure requiring treatment (defined as left ventricular ejection fraction $\leq 45\%$) *
- Onset of pulmonary arterial hypertension requiring right heart catheterization *

* Caused by SSc

10.1.6 The Number of Digital Ulcers

The investigator or subinvestigator will count the number of digital ulcers.

10.1.7 Patient-reported outcome

- 1) HAQ-DI

Participants will assess the degree of their difficulty in performing actions of eight functional categories (dressing and grooming, arising, eating, walking, hygiene, reach, grip, and activities) using HAQ-DI (Health assessment questionnaire disability index, Japanese version)⁹⁾ on a 4-point scale of 0 (Without any difficulty), 1 (Without some difficulty), 2 (Without much difficulty), and 3 (Unable to do).

2) FACIT-Fatigue

Participants will assess their fatigue over the past 7 days using FACIT-Fatigue Scale, Japanese version¹⁰⁾ on a 5-point scale from 0 (not at all) to 4 (very much).

3) FSSG.

Participants will assess their gastroesophageal reflux disease using Frequency Scale for the Symptoms of GERD (FSSG)¹¹⁾ on a 5-point scale from 0 (never) to 4 (always).

10.1.8 Global improvement rating

1) PtGA

Participants will assess their general health status associated with SSc at visit using a 10-cm visual analog scale (VAS) from 0 (the best status) to 10 (the worst status)¹²⁾. The investigator or subinvestigator or the clinical trial collaborator will measure the length (cm) from the left end to the first decimal place and record it.

2) PGA

The investigator or subinvestigator will assess participants' general health status associated with SSc in terms of Severity, Damage, and Overall disease using a 10-cm VAS from 0 (the best status) to 10 (the worst status)¹²⁾. The investigator (or subinvestigator) or the clinical trial collaborator will measure and record the length (cm) from the left end to the first decimal place.

10.2 Efficacy Endpoints

10.2.1 Primary Endpoint

Change from baseline in mRSS at Week 24

10.2.2 Other Endpoints

- 1) Change from baseline in mRSS at Week 52
- 2) Change from baseline in HAQ-DI at Week 52
- 3) Change from baseline in HAQ-DI at Week 24
- 4) Change from baseline in %FVC at Week 52
- 5) Change from baseline in %FVC at Week 24
- 6) Change from baseline in DLco at Week 52
- 7) Change from baseline in DLco at Week 24
- 8) Change from baseline in PGA at Week 52
- 9) Change from baseline in PGA at Week 24
- 10) Change from baseline in PtGA at Week 52
- 11) Change from baseline in PtGA at Week 24
- 12) ACR-CRISS at Week 52
- 13) ACR-CRISS at Week 24
- 14) Change from baseline in the number of digital ulcers at Week 52

- 15) Change from baseline in the number of digital ulcers at Week 24
- 16) Time-course changes in the following parameters:
 - a) HAQ-DI
 - b) FACIT-Fatigue
 - c) FSSG
 - d) FVC
 - e) %FVC
 - f) DLco
 - g) %DLco
 - h) TLC
 - i) FEV₁
 - j) Severity assessment of lung lesion
 - k) PGA
 - l) PtGA
 - m) ACR-CRISS
 - n) The number of digital ulcers

